8.4.6.2 Biochemistry

Biochemistry parameters (blood urea nitrogen, creatinine, total bilirubin, sodium, potassium, chloride, calcium, aspartate transaminase (AST), alanine transaminase (ALT), alkaline phosphatase (ALP), albumin, total protein, glucose, magnesium, phosphates) will be evaluated over time. The baseline evaluation for each parameter will be the final evaluation prior to the OTL-101 infusion.

For each parameter, the actual value and change from baseline will be summarized at each visit using descriptive statistics.

Biochemistry evaluations will be flagged against the normal range as low/normal/high. For each parameter, the number (%) of subjects with evaluations that were low/normal/high relative to the normal range will be summarized by visit. In addition, shift tables will be constructed comparing the flags at the baseline evaluation with the minimum and maximum evaluation post-infusion. Out of range values will be assessed for their clinical significance. For each parameter, the number (%) of subjects with clinically significant evaluations will be summarized by visit and at any time post-infusion.

8.4.7 Vital Signs, Height and Weight

Vital signs (temperature, pulse rate, respiratory rate, systolic and diastolic blood pressure and oxygen saturation), height and weight are measured over time.

The baseline evaluation for each of the vital signs, height and weight will be the final evaluation prior to the OTL-101 infusion.

For each parameter, the actual value and change from baseline will be summarized at each visit using descriptive statistics.

Any vital signs found to be out of range will be categorized as not clinically significant or clinically significant. For each vital sign, the number (%) of subjects with clinically significant evaluations will be summarized by visit and at any time post-infusion.

8.4.8 Physical Examination

Physical examinations will be performed over time. The number (%) of subjects with abnormal evaluations will be summarized by body system at each visit. An overall summary will also be produced for each body system showing the number (%) of subjects with normal evaluations at all pre-treatment evaluations who had one or more abnormal evaluations post-treatment.

9 Analysis Software

All summaries and analyses will be carried out using SAS® version 9.4.

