- 6) As thawed OTL-101 is infused, an unusual odor or bad taste in the mouth may be experienced. This odor or taste is from the substance dimethylsulfoxide (DMSO) used to protect the cells when OTL-101 is cryopreserved. Some subjects may cough or feel slightly nauseated or chilled when they receive thawed product containing DMSO. In rare cases, DMSO may cause side effects such as low blood pressure, fast heart rate, or shortness of breath. Subjects will be monitored closely during the OTL-101 infusion.
- 7) Immune response against "normal" ADA – as a result of "immunisation" to normal human ADA produced from the transgene. Most subjects will have previously received bovine PEG-ADA ERT, which is more likely to be immunogenic than human ADA. Also, development of significant inhibitory antibodies has been relatively rare in patients treated with PEG-ADA ERT alone.
- 8) Other immunological risks - onset of autoimmunity is of concern in post-treatment ADA-SCID patients.
- 9) Immune dysregulation - gene transfer research may result in only partial improvement of the immune system. While this is unlikely to be a problem, it is possible that partial improvement leading to an "imbalance" of the immune system could have adverse effects. Two children treated in the UCLA study using fresh OTL-101 formulation developed an inflammatory response with fevers and rashes requiring hospitalization about 4-12 months post OTL-101 infusion. This reaction may have been associated with the response to gene therapy treatment, with temporary immune dysregulation occurring as the immune system developed. Both children were treated with steroids and have fully recovered, suggesting the inflammatory reaction may be temporary. Both children remain free of PEG-ADA therapy.
- 10) Failure of the treatment.

These risks are fully described in the IB.

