- Physical examination, including the recording of height (cm), weight (kg), and vital signs (temperature, pulse rate, respiratory rate and blood pressure). Temperature can be measured as per standard clinic practice.
- Blood tests:
 - o Biochemistry (see [Table 3](#)),
 - o Hematology (see [Table 3](#)),

- Prothrombin Time or INR and PTT,
- Peripheral blood or bone marrow for cytogenetic analysis (if cytogenetic testing has not been performed on cells from amniocentesis) by karyotype, Comparative Genome Hybridization (CGH), whole exome sequencing (WES) or other and may be used independently from the time they have been performed,
- HIV-1, HepB and ParvoB19,
- Serum human chorionic gonadotropin (HCG) pregnancy test, if the subject is a female of child-bearing age (to be performed within 30 days of Visit 1),
- Urinalysis,
- Electrocardiogram,
- Echocardiogram,
- Chest X-ray (+/- computer tomography (CT) scan if previous evidence of severe chest disease),
- Pulse oximetry,
- Biopsy of any suspicious skin lesions,
- Evaluation of quality of life, as measured by the Karnofsky/Lansky scale and questions relevant to general well-being, school attendance, and ability to practice sports, respectively,
- Evaluation of severe infections or opportunistic infectious episodes.

In addition, the collection of AEs and concomitant medication will start after signature of the informed consent form.

If a subject meets the eligibility criteria, he/she will be enrolled and scheduled for CD34+ HSCs harvest.

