8.3 Physical Examination

Physical examinations, including weight (kg) and body height (cm) will be conducted at times indicated in [Table 1](#) and [Table 2](#).

Any clinically significant physical examination findings (abnormalities) observed during the study will be reported as AEs. Any physical examination findings (abnormalities) persisting at the end of the study will be followed by the Investigator until resolution or until reaching a clinically stable endpoint.

A review of all body systems will include the following:

- General appearance
- Skin
- Head, including ears, eyes, nose, throat, if feasible.
- Respiratory
- Cardiovascular
- Abdomen (including liver and kidneys)
- Neurological examination with sensory testing

Any abnormalities or changes in intensity noted during this review of body systems should be documented in the source document and reported appropriately in the eCRF. In addition, the resolution of any abnormal findings during the study will be noted in the source document and eCRF, if clinically significant.

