9.6.5 Safety Analyses

All AEs will be coded according to the current Medical Dictionary for Regulatory Activities (MedDRA) version and will be classified by MedDRA preferred term and system organ class. AE listings will be presented by subject, system organ class and preferred term. Incidence of treatment emergent AEs (TEAE) and SAEs will be tabulated by system organ class and preferred term. In addition, summary tables will be presented by maximum severity, relationship to treatment and TEAEs associated with premature withdrawal from the study.

A TEAE is defined as any AE that occurs during the active phase of the study if:

- it was not present prior to receiving the OTL-101 infusion, or
- it was present prior to receiving the OTL-101 infusion but the intensity increased during the active phase of the study, or
- it was present prior to receiving the OTL-101 infusion, the intensity is the same but the drug relationship became related during the active phase of the study.

Summary statistics (mean, median, SD and range as appropriate) will be presented for vital signs, ECG parameters and clinical laboratory tests at each assessment along with change from baseline. For laboratory data, abnormal values will be flagged in the data listings. Shift tables will be presented of the number and percentage of subjects with low, normal or high values and normal or abnormal examinations at each visit and overall.

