8.4.6 Laboratory Evaluations

8.4.6.1 Haematology

Haematology parameters (red blood cell (RBC) count, hemoglobin, hematocrit, mean corpuscular volume (MCV), mean corpuscular hemoglobin (MCH), mean corpuscular hemoglobin concentration (MCHC), white blood cell count (WBC), neutrophils, lymphocytes, monocytes, eosinophils, basophils and platelet count) will be evaluated over time. The baseline evaluation for each parameter will be the final evaluation prior to the OTL-101 infusion.

For each parameter, the actual value and change from baseline will be summarized at each visit using descriptive statistics.

Hematology evaluations will be flagged against the normal range as low/normal/high. For each parameter, the number (%) of subjects with evaluations that were low/normal/high relative to the normal range will be summarized by visit. In addition, shift tables will be constructed comparing the flags at the baseline evaluation with the minimum and maximum evaluation post-infusion. Out of range values will be assessed for their clinical significance. For each parameter, the number (%) of subjects with clinically significant evaluations will be summarized by visit and at any time post-infusion.

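### SAP 8.4.8 omits the physical-examination shift table that Protocol 9.6.5 calls for, and its overall summary leaves out some findings that are new after infusion

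*SAP*

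**What the plan says.** SAP 8.4.8 plans two outputs. The first has no pre-treatment condition: "The number (%) of subjects with abnormal evaluations will be summarized by body system at each visit". The second is an overall summary for each body system, "showing the number (%) of subjects with normal evaluations at all pre-treatment evaluations who had one or more abnormal evaluations post-treatment". Its denominator is not stated.

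Protocol 9.6.5 plans something different: "Shift tables will be presented of the number and percentage of subjects with low, normal or high values and normal or abnormal examinations", both by visit and in total. The SAP keeps shift tables for laboratory data. SAP 8.4.6.1 says "shift tables will be constructed comparing the flags at the baseline evaluation with the minimum and maximum evaluation post-infusion", and SAP 8.4.6.2 does the same for biochemistry. No shift table is planned for physical examination.

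For haematology, biochemistry, vital signs and quality of life (SAP 8.4.6.1, 8.4.6.2, 8.4.7 and 8.3.2.3), baseline is the last evaluation before infusion. SAP 8.4.8 alone looks back over every earlier examination.

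On data collection, Protocol 8.3 states: "Any abnormalities or changes in intensity noted during this review of body systems should be documented".

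**The concern.** A safety reader wants to know which findings appeared or worsened after infusion. In the SAP, only the overall summary tries to answer this, and its condition is stricter than the baseline rule used elsewhere. One abnormal result at any pre-treatment examination removes the subject from that body system's count, even if the finding had cleared before infusion. If a new abnormality then appears, it is not counted as new.

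The protocol's shift table would show that subject as moving from normal to abnormal. Without it, the by-visit counts show that an abnormality exists but not whether it was there before. What is at stake is an undercount of new findings in a descriptive safety table. No primary endpoint or stopping rule depends on it.

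**Working it through.** The plan states no figure on this point, so the check compares the texts and then illustrates the effect.

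**Step 1: pre-treatment examinations.** Three are scheduled:
- screening (Protocol 5.1.1: "Physical examination, including the recording of height (cm), weight (kg), and vital signs")
- pre-harvest, Assessment A (Protocol 5.1.2)
- baseline, Assessment C, after harvest and in the week before the first Busulfan dose (Protocol 5.1.3).

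**Step 2: does the protocol's shift table cover physical examination?** Protocol 9.6.5 speaks of examinations without naming the type, so this is an inference. It is a reasonable one. Protocol 8.3 records physical findings as abnormalities over repeated visits, whereas SAP 8.2.8 takes the ECG only at screening, so no ECG shift across visits is possible.

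**Step 3: which histories can be counted?** Write N for normal and A for abnormal, in time order. Three examinations give 2³ = 8 histories.
- SAP 8.4.8 admits one: NNN.
- A baseline at the last examination admits four as normal at baseline: NNN, ANN, NAN and AAN.
- The two rules differ on ANN, NAN and AAN. A subject with one of these histories and an abnormal result after infusion is new under the shift table and absent from the SAP's overall count.

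**Step 4: illustration of size.** Let p be the chance that a body system is abnormal at any one pre-treatment examination. The documents do not give p, so the values below are assumptions, taken as equal at all three examinations. If examinations are independent, the SAP rule bars 1 − (1 − p)³ of subjects and the last-examination rule bars p. The number of subjects is 10 (Protocol 9.4).

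| p (assumed) | Barred by SAP rule | Barred by last-examination rule | Difference | Difference in 10 subjects |
|---|---|---|---|---|
| 0.05 | 14.3% | 5% | 9.3% | 0.9 |
| 0.10 | 27.1% | 10% | 17.1% | 1.7 |
| 0.20 | 48.8% | 20% | 28.8% | 2.9 |
| 0.30 | 65.7% | 30% | 35.7% | 3.6 |

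If a finding present at one examination is present at all three, both rules bar the same subjects and the difference is zero. Examinations of one child over a short period are likely to be correlated, so independence overstates the gap. The undercount itself is smaller again, because a barred subject matters only if that system is abnormal after infusion.

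**Step 5: denominator.** At p = 0.20 under independence, the percentage could be taken over all 10 treated subjects or over the 10 × 0.8³ ≈ 5 who were normal throughout. SAP 8.4.8 does not say which.

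**The case against.** The strongest defence is that requiring normality at every earlier examination is a strict but legitimate definition of a new abnormality, offered beside unrestricted by-visit counts in a ten-subject descriptive study. That is fair as far as it goes. It does not explain why the protocol's shift table is missing, or why this section departs from the baseline rule used elsewhere in the SAP.

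Several stronger readings are tempting, and the documents do not support them.

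- **That a child with an earlier abnormality can never show a new finding.** The bar applies to one table and, within it, to one body system. The by-visit counts still include the child.
- **That a serious reaction would go unreported.** Protocol 1.4.2.1 describes two children given the fresh product who "developed an inflammatory response with fevers and rashes requiring hospitalization about 4-12 months post OTL-101 infusion". A similar case would appear in the by-visit counts. Being hospitalised, it would be a serious adverse event (Protocol 8.2.3), and with onset after infusion it would be treatment-emergent (SAP 8.4.1.1). Clinically significant examination changes are also recorded as adverse events (Protocol 8.2.1.5 and 8.3). This route is weaker for pure worsening, because SAP 8.4.1.1 goes by onset and lacks the increased-intensity condition in Protocol 9.6.5.
- **That harvest or catheter sites will commonly bar children, or that the rule omits the sickest.** The baseline examination does follow harvest, but nothing says such sites are scored abnormal or how often systems are abnormal before treatment.
- **That the SAP drops the protocol's shift tables altogether.** It keeps them for haematology and biochemistry.

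One further objection stands. A normal/abnormal shift table would show a child already abnormal at Assessment C as abnormal before and after, so it cannot reveal a different or worse finding in that system. The shift table alone is therefore not a full remedy.

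**Conclusion.** The point holds as a gap between protocol and SAP in descriptive safety reporting. The SAP lacks the examination shift table, and its one linked summary misses subjects who were abnormal earlier, normal at the last pre-infusion examination and newly abnormal afterwards.

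The size cannot be fixed from the documents. A reader might take the 27% to 66% barred at p = 0.10 to 0.30 as the loss. Those are gross figures under assumed rates and independence, and a last-examination baseline would itself bar 10% to 30%. The net difference runs from zero under full persistence to about 36% of subjects per body system at p = 0.30, before allowing for whether anything abnormal follows. It may be small in practice.

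The conclusion rests on reading the examinations in Protocol 9.6.5 as including physical examinations. No efficacy conclusion is affected.

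**What to change.** In SAP 8.4.8:

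1. Add a shift table by body system for all treated subjects, from the final pre-infusion examination to each post-infusion visit and to the worst post-infusion status.
2. State the denominator of the overall summary if it is kept.
3. Because a normal/abnormal table cannot show worsening, also report the number and percentage of subjects with a new or worsened finding in each body system, using the abnormalities and intensity changes that Protocol 8.3 already requires to be documented.

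The cost is a change of SAP wording, one shift table and one count per body system. No further examinations or data are needed.
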